## **VI. Biostatistical Analyses:**

The baseline data to be collected and analyzed include: subject age at enrollment, gender, age of depression onset, number of previous depressive episodes, HDRS. HDRS will be repeated at the subsequent study visits for analysis. Cytokine levels will also be analyzed at the initial and final visits. The planned study end-point is at eight weeks after initiation, and is not based on any pre-determined treatment response. Exploratory analysis of the immunologic profiling data will be performed as well, with a goal to detect within-subject changes over the course of the study and to discern any differences between non-responders and responders.

Baseline measurements for continuous variables (e.g., age of onset, current age) will be assessed by t-test. Categorical measurements, such as gender, will be compared with Fisher's exact test or chi-square as appropriate. For the primary study outcome, the change in HDRS in the treatment versus control groups will be evaluated with analysis of covariance (ANCOVA), with initial HDRS score as a covariate.

Power calculations were based on a prior open-label trial of salicylic acid as an augmentation agent to fluoxetine, which found an average 15-point drop in HDRS score over a 4-week trial. To be conservative, we are assuming a much smaller effect size, and so this study is powered to detect a 3-point difference in HDRS score, a difference which is deemed to be clinically significant. 29 participants per group are required to detect this clinically significant difference assuming .80 power and a two-sided alpha of 0.05. Assuming a non-completion rate of approximately 20%, customary in clinical trials of antidepressants, we will enroll 74 subjects, anticipating 60 completers.

Secondary outcomes will include the response of inflammatory biomarkers in treatment responders v. treatment non-responders at 8 weeks and the degree of biomarker association with antidepressant response. For this, the association of IL-6 and TNF- $\alpha$  at V1 with change in HDRS from V1 to V4 in the aspirin treated group versus the placebo treated group will be evaluated with an analysis of covariance (ANCOVA) model. This model will include three variables: treatment condition (aspirin versus placebo), baseline IL-6 or TNF- $\alpha$  level, and an interaction term (baseline cytokine value x treatment). A similar analysis of change in HDRS scores will be performed to assess the interaction of baseline TNF- $\alpha$  to IL-10 and IL-6 to IL-10 ratios by treatment condition. All applicable tests will be two-tailed with an alpha set at 0.05.

For our exploratory analysis of the full panel of 60 cytokines and chemokines, we expect to perform 60 comparisons and plan to use a false discovery rate approach. The interaction of the baseline value of each cytokine or chemokine with treatment condition will be evaluated. The interaction  $p$  values will be converted to FDR *adjusted p* values and ordered from smallest to largest. A cut point of 10% will be used to control the false discovery rate and to identify a subset of values that will be presumed to be biologically relevant. A similar procedure will be carried out for analysis of the 96 immune genes. All analyses were designed in consultation with a biostatistician.

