## **IX. Monitoring and Quality Assurance:**

The principal investigator, [name], will be responsible for monitoring the safety of all subjects. In the event that [name] is unavailable, physician co-investigators will be available to monitor the safety of all subjects.

All study staff are primarily located at Brigham and Women's Hospital. Study safety meetings, including the principal investigator, study coordinators, and study physicians will occur regularly to review the progress of currently-enrolled subjects and any reported side effects.

The Principal Investigator will assess all patients with regard to stopping criteria. In general terms, a subject will be discontinued from the study for the following reasons:

- 1) The subject has experienced an adverse event that, in the opinion of the principal investigator requires early termination
- 2) The subject's thoughts or behaviors become a safety risk at any time during the trial
- 3) The subject experiences a 20% drop in GFR during the course of the study
- 4) The subject withdraws consent

Specific to this study, subjects will be monitored for suicidal thoughts at both visits and for adverse events as well. Subjects who develop active suicidal ideation, represented by a score of  $>2$  on HDRS item 3, will be referred for urgent or emergent clinical assessment. A patient who develops active suicidal thoughts will be urgently evaluated by a study physician. In any case where there are acute safety concerns arising from suicidality (such as a plan or actual intent), the patient will be sent to the BWH Emergency Department for further evaluation under Section 12a, and in compliance with hospital policies. If there are no acute safety concerns based on the urgent evaluation, the patient will be monitored according to study protocol and instructed to contact study staff immediately with any worsening in their mood or thinking. The study physician will review the urgent or emergent safety assessment and determine if the subject can continue in the study. Any subject who requires a level of care exceeding customary outpatient services (i.e., psychiatric hospitalization or participation in a partial hospital program) will be removed from the study. If a subject must be transferred from the study into clinical care, the study physicians will continue to follow the subjects until they are accepted into appropriate, longer-term care, if clinically indicated.

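### The primary ANCOVA of HDRS change names no analysis set or missing-data method despite about 20% expected loss, and no stated model uses the week 2 and 4 scores; naming an all-randomized analysis that uses them is a cheap improvement

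*Combined protocol and SAP*

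**What the plan says.** Section VI (Biostatistical Analyses) states the primary analysis in one sentence: "the change in HDRS in the treatment versus control groups will be evaluated with analysis of covariance (ANCOVA"), with the initial score as covariate. The sentence gives neither a visit nor a population. Week 8 has to be inferred from "The planned study end-point is at eight weeks after initiation" and from the secondary biomarker models, which use "change in HDRS from V1 to V4 in the aspirin treated group versus the placebo treated group".

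The sample size rests on completers: "29 participants per group are required to detect this clinically significant difference", and, after allowing for about 20% non-completion, "we will enroll 74 subjects, anticipating 60 completers".

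HDRS is rated at weeks 2 and 4 (Section V, Study Visit 2 and 3), and Section VI says "HDRS will be repeated at the subsequent study visits for analysis". No model in Section VI uses those two scores. Aim 1b, on rapidity of change, has no analysis there either. No section names an analysis set, a missing-data method or a sensitivity analysis, and no HDRS rating is planned after a subject is discontinued.

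**The concern.** A subject with no week-8 score contributes nothing to an ANCOVA of week-8 change unless a rule says how the score is replaced. The plan expects this for about one subject in five and gives no rule. Applied as written, the model compares those who stayed, which is not the comparison that was randomized.

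Whether that matters depends on why subjects leave. If leaving is related to HDRS more strongly in one arm, the subjects who stay are a differently selected group in each arm, and the week-8 difference is shifted. The week 2 and 4 scores carry the information needed to correct for loss that follows observed HDRS. They are already scheduled but unused. An unstated method can also be settled after the data are seen.

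**Working it through.** **1. The plan's own figures.** With n per group = 2(1.960 + 0.842)² SD²/Δ² and Δ = 3, the documents' 29 per group cannot be reproduced directly because no SD is given. Solving for it: SD = 3 × √(29/(2 × 7.849)) = 4.08. The same formula with 28 gives 4.01, so 29 corresponds to an SD of about 4.0 to 4.1. Enrolment is consistent: 29/0.80 = 36.25, hence 37 per group and 74 in all; 74 × 0.80 = 59.2, near the 60 completers stated. Expected loss is 74 × 0.20 = 14.8, about 15 subjects.

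**2. When complete-case analysis is biased.** In each arm let f be the fraction lost and G the baseline-adjusted mean week-8 score of leavers minus that of stayers. Then mean of stayers = mean of all − f × G, so

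complete-case difference (aspirin − placebo) = true difference − f_A G_A + f_P G_P.

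- Random loss: both G are 0, so no bias.
- Equal f and equal G: the terms cancel.
- Placebo only, f_P = 0.20: a gap of 2 points shifts −3.0 by 0.20 × 2 = 0.4, to −2.6; a gap of 4.75 points shifts it by 0.95, to −2.05.
- Aspirin only: the same shift with the opposite sign, for example −3.4 in place of −2.6.

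**3. Simulation.** All of these inputs are assumptions: 37 per arm; 20% loss per arm; true difference −3.0, with 50/75/100% of it present at weeks 2/4/8; HDRS SDs 3.5/5.5/6/6.5 at weeks 0/2/4/8, or the same set scaled to a week-8 SD of 4.07; correlations 0.5, 0.4 and 0.3 of baseline with weeks 2, 4 and 8, 0.7 (weeks 2–4), 0.6 (weeks 2–8) and 0.75 (weeks 4–8). Loss after week 2 or 4 is logistic in the standardized HDRS change at that visit on placebo, and random on aspirin.

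| Log-odds of loss per SD, placebo | Complete-case, SD 6.5 | Complete-case, SD 4.07 | Likelihood using weeks 2, 4, 8 |
|---|---|---|---|
| 0 (random) | −3.0 | −3.0 | −3.0 |
| 0.5 | −2.6 | −2.75 | about −3.0 |
| 1.0 | −2.3 | −2.5 to −2.6 | about −3.0 |
| 1.5 | −2.05 | −2.4 | about −3.0 |

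At log-odds 1.0, power is about 30% for complete-case against 47% for likelihood (SD 6.5), and 71% against 86% (SD 4.07). With no true effect, complete-case rejects in about 7% of trials at 1.0 and 9% at 1.5. Nearly all of these rejections go against aspirin; fewer than 1% of trials favour it. If half the loss is random and before week 2, the complete-case estimates are −2.8 / −2.9 at 0.5 and −2.4 / −2.6 at 1.5 (SD 6.5 / 4.07). Equal dependence with equal loss in both arms gives −3.0.

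**4. Precision under random loss.** The standard error falls from 1.63 to 1.57 (SD 6.5) and from 1.02 to 0.98 (SD 4.07). The squared ratios of these rounded values are 1.078 and 1.083, so the gain is roughly 7 to 8% more information. Taking power as Φ(3/SE − 1.96), it moves from 0.452 to 0.480 and from 0.837 to 0.865, about 2.8 points each. If half the loss precedes week 2, the information gain is 3 to 4%. If all of it does, there is none. At the favourable extreme (correlation 0.8 between all visits, all loss after week 4), effective n per arm rises from 29.6 to 34.5, and power from 81.3% to 86.8% at residual SD 4.05.

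**5. What the better model does not cure.** If placebo loss depends on the unseen week-8 score, the likelihood estimate is itself biased: −2.7 / −2.8 at log-odds 0.5 and −2.1 / −2.5 at 1.5 (SD 6.5 / 4.07).

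**The case against.** Baseline-adjusted ANCOVA is a standard primary analysis, and under random loss, or equal dependence with equal loss, it gives the right answer at a small cost in power. This stands. The larger shifts come from stress tests: log-odds of 1.0 to 1.5 on placebo with none on aspirin. At 0.5 the shift is 0.25 to 0.4 points against a standard error of 1.0 to 1.6. This also stands.

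Three stronger readings are tempting, and the documents do not support them.

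- A reader might infer that the plan commits to a completers analysis. Sizing on completers and the V1-to-V4 wording make that the natural reading, but no sentence says so; carry-forward or imputation would also fit.
- A reader might infer that the stopping rule "The subject experiences a 20% drop in GFR during the course of the study" (Section IX) removes more aspirin subjects and so biases the result. A fall in GFR is not an HDRS event, and loss unrelated to HDRS does not bias the estimate even when unequal. A fall found in the week-8 bloods comes at the same visit as the week-8 HDRS. The rule should not be cited as a source of bias.
- A reader might take removal of subjects needing a higher level of care ("psychiatric hospitalization or participation in a partial hospital program) will be removed from the study") as proof of loss that a repeated-measures model repairs. It does tie loss to worsening, but it applies to both arms, and deterioration between visits may not show in the last observed score. That is closer to the case the model does not cure.

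**Conclusion.** The point holds as a cheap improvement, not as an error in the ANCOVA. The plan leaves the population and missing-data method open for about 15 of 74 subjects and leaves collected HDRS scores out of every stated model.

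If loss is benign, the cost is about 2 to 3 points of power, less if loss is early. If loss follows observed HDRS on placebo only, a true −3.0 is estimated as about −2.6 to −2.05 (SD 6.5) or −2.75 to −2.4 (SD 4.07); the consequences are lost power and false signals against aspirin, not false claims of benefit. Aspirin-only dependence reverses the sign and favours aspirin. These sizes rest on assumed SDs, correlations and dropout models; the documents give no SD and no dropout pattern by arm, so bias is possible but not shown. Confidence is medium.

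**What to change.** Before unblinding, state in Section VI:

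1. **Primary analysis.** All randomized subjects, as assigned. HDRS change at weeks 2, 4 and 8 in a repeated-measures model with treatment, visit, treatment × visit, baseline HDRS and baseline × visit; unstructured covariance; primary contrast aspirin minus placebo at week 8. ANCOVA after multiple imputation that uses the week 2 and 4 scores serves equally well. What matters is that one is named in advance.
2. **Sensitivity analysis.** One delta-adjusted analysis by arm, because neither method corrects for loss driven by unseen scores.
3. **What is estimated.** Without scores after discontinuation, the model estimates what leavers would have scored had they followed similar subjects who stayed. Say so.

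The cost is SAP wording and a slightly more complex model; the scores are already scheduled, so no subjects or visits are added. There is little gain if loss is random or mostly before week 2.

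Two separable options:

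- **Week-8 ratings from early leavers**, where consent allows. This is at most about 15 ratings, but it is a procedure change: Section V offers remote ratings only at weeks 2 and 4, and Section IX removes some subjects from the study. Discontinuation criteria would stay as they are.
- **Aim 1b** from the same model: the between-arm difference gained in weeks 0–4 minus that gained in weeks 4–8, with a confidence interval. With 30 per arm and a 3-point effect, power is 11% / 21% (SD 6.5 / 4.07) if 75% of the effect arises by week 4 and 31% / 65% if all of it does; the interval half-width is about 4.0 / 2.5 points. It should be presented as an estimate with low power.

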## **Hypotheses:**

Peripheral inflammatory mediators are differentially expressed in sub-populations of depressed patients, and such differences may represent indicators of responsiveness to anti-inflammatory treatment approaches.

**1a:** That aspirin augmentation will decrease HDRS scores versus placebo augmentation, and that a responder subgroup within the aspirin augmentation group will account for most of this signal.

**1b:** That aspirin augmentation will exert most of its clinical effect (steepest slope of change in HDRS) during the first 4 weeks of treatment.

**2:** That the serum inflammatory profile of the aspirin augmentation responders differs from the non-responders.

**2a:** That elevated IL-6 and TNF- $\alpha$  at study initiation will be associated with treatment response to aspirin.

**2b:** That IL-6 and TNF- $\alpha$  will be lower in the augmentation responders group versus the non-responders group after treatment.

**2c:** That higher ratios of TNF- $\alpha$ :IL-10 and IL-6:IL-10 will be associated with greater treatment response to aspirin.

**3:** That there will be different patterns of immunologic activation between treatment responders and non-responders, and within the treatment-responders group before and after treatment with aspirin.

**3a:** That the cytokines/chemokines assessed will show a different pattern of elevations in the aspirin-responder versus the aspirin non-responder group pre-treatment, and that the aspirin-responder group will show a differential pattern post- versus pre-treatment.

**3b:** That the peripheral inflammatory transcriptome will show altered patterns of immune gene expression in the aspirin-responder versus the aspirin non-responder group pre-treatment, and that the aspirin-responder group will show a differential pattern of gene expression post- versus pre-treatment.

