## **III. Subject Selection:**

This study is a randomized, double-blind, placebo-control trial. The trial will enroll 74 adult subjects with treatment-refractory major depressive disorder, 37 per group. Assuming a non-completion rate of approximately 20%, as is customary in clinical trials of antidepressants, we will enroll a total of 74 subjects, anticipating 60 study completers. Subjects will all be recruited through outpatient psychiatric clinics affiliated with Brigham and Women's Hospital, through physician referral, print advertisements, and flyers.

Inclusion criteria:

- Aged 18-55
- Current diagnosis of major depressive disorder
- Hamilton Depression Rating Scale score of  $\geq 21$

- Stable treatment regimen (no medication changes or changes in psychotherapy treatment in past 8 weeks, and no participation in stepped treatments, such as completion of a course of cognitive behavioral therapy, during the trial)
- Failed to remit with up to 2 sequential antidepressant trials, or combination of 1 antidepressant and 1 augmentation agent
- Women of childbearing age must agree to use an approved method of contraception for the duration of the study

Exclusion criteria:

- Active suicidal ideation
- History of manic episodes or psychosis
- Alcohol or substance use disorder within the past 6 months
- Comorbid neurologic condition affecting the central nervous system
- Comorbid autoimmune condition
- History of thyroid disease or a current abnormal TSH
- Active or recent (within the past month) infection (such as otitis, pneumonia, urinary tract infection); temperature  $> 100.3$  or WBC count  $> 11$  K/microL will be considered evidence of active infection even in the absence of other symptoms
- History of GI bleed
- History of stroke
- History of a bleeding disorder
- Platelet count  $< 150,000/\text{mm}^3$  on initial screening
- On a blood-thinning agent or taking NSAIDs daily
- Current use of oral steroids or other immunomodulating medications
- Salicylate sensitivity
- Pregnancy or breastfeeding
- GFR less than  $60 \text{ mL/min}/1.73\text{m}^2$
- Current use of another nephrotoxic medication

The decision not to restrict participation to subjects utilizing a single medication was made to better reflect clinical practice, in which a variety of SSRI (selective serotonin reuptake inhibitors) and SNRI (serotonin-norepinephrine reuptake inhibitors) are used as first-line agents, and in order to enhance the generalizability of study findings.

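### Does the missing standard deviation, read with Hypothesis 1a, mean that 29 per group falls short of the stated 80% power for a 3-point HDRS difference?

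*Combined protocol and SAP*

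**What the plan says.** Section VI (Biostatistical Analyses) states that "this study is powered to detect a 3-point difference in HDRS score" and that "29 participants per group are required to detect this clinically significant difference assuming .80 power and a two-sided alpha of 0.05". It names its source: "Power calculations were based on a prior open-label trial of salicylic acid as an augmentation agent to fluoxetine". From that trial it reports only an average fall of 15 points over 4 weeks, and it then adopts 3 points as a deliberately smaller target. No SD, standardised effect or correlation between baseline and outcome appears there or elsewhere in the document.

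For the primary outcome, the change in HDRS "will be evaluated with analysis of covariance (ANCOVA), with initial HDRS score as a covariate".

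Section III (Subject Selection) gives the size: "The trial will enroll 74 adult subjects with treatment-refractory major depressive disorder, 37 per group". Both sections assume about 20% non-completion and expect 60 completers.

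Hypothesis 1a, in the list that follows the Specific Aims, expects aspirin to lower HDRS scores relative to placebo and adds that "a responder subgroup within the aspirin augmentation group will account for most of this signal".

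**The concern.** A sample size for a difference in means needs four inputs: difference, alpha, power and SD. The plan gives three. Its named source contributes a mean fall within a single open-label group, which supplies neither a between-group difference nor a spread. The number that sizes the trial therefore cannot be derived from the text, and a reader who works backwards finds that it needs an SD of about 4 points.

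Hypothesis 1a seems to make this worse. If only some aspirin patients benefit, the aspirin arm becomes more variable than the placebo arm, and an SD that was adequate for a uniform 3-point shift may no longer be. If power were really nearer 50% than 80%, a null result would say little about a 3-point benefit, although the plan describes the trial as powered for one.

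**Working it through.** **Inputs from the documents.** Difference 3 points, two-sided alpha 0.05, power 0.80, 29 per group, 1:1 allocation, about 20% dropout, 74 enrolled, 60 completers expected (Sections III and VI). The SD is not given.

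**Reproducing the 29.** For a two-sample t-test with n per group, the noncentrality is (3/SD) × √(n/2), on 2n − 2 degrees of freedom. Take SD 4.0 as a trial value:
- n = 28: power 78.7%.
- n = 29: noncentrality 0.75 × √14.5 = 2.86, power 80.1%.

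So SD 4.0 returns exactly 29. Solving for the largest SD that keeps 80% power gives 4.01 at 29 per group and 4.08 at 30. Deducting one degree of freedom for the covariate leaves both unchanged to two decimals.

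**Dropout.** 29/0.8 = 36.25, which rounds up to 37 per group and 74 in total, as stated.

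**What 4.0 means under ANCOVA.** Adjustment for baseline makes the relevant SD a residual one. With baseline–outcome correlation r, the raw SD that leaves a residual of 4.0 is 4.0/√(1 − r²). This is 4.19 at r = 0.3, 4.62 at 0.5, 5.00 at 0.6 and 5.60 at 0.7. These correlations are assumptions, as the plan states none.

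**Sensitivity to the SD.** All SDs here are assumed.

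| SD | Power, 29 per group | Power, 30 per group |
|---|---|---|
| 4.0 | 80% | 81% |
| 4.5 | 70% | 72% |
| 5 | 61% | 63% |
| 6 | 46% | 48% |
| 7 | 36% | 37% |
| 8 | 29% | 30% |

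**Hypothesis 1a.** Suppose a share p of the aspirin arm carries a fraction f of the 3-point mean effect. Responders gain 3f/p and the others gain 3(1 − f)/(1 − p). Let g be the gap between these two gains. The aspirin-arm variance then rises by p(1 − p)g². With an SD of 4.0 in the placebo arm and within each subgroup, the pooled SD is √(16 + p(1 − p)g²/2).

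Example, p = 1/2 and f = 0.7: g = 4.2 − 1.8 = 2.4, added variance 0.25 × 5.76 = 1.44, pooled SD √16.72 = 4.09.

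| p | f | Pooled SD | Power, 29 per group | Power, 30 per group |
|---|---|---|---|---|
| 1/2 | 0.6 | 4.02 | 79.7% | 81.1% |
| 1/2 | 0.7 | 4.09 | 78.4% | 79.8% |
| 1/3 | 0.6 | 4.18 | 76.7% | 78.1% |
| 1/3 | 0.7 | 4.33 | 73.7% | 75.2% |
| 1/4 | 0.8 | 4.82 | 64% | 66% |
| 1/2 | 1 | 4.53 | 70% | 71% |
| 1/3 | 1 | 5.00 | 61% | 63% |
| 1/4 | 1 | 5.43 | 54% | 56% |
| 1/5 | 1 | 5.83 | 49% | 50% |

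The last four rows put the whole effect in the subgroup, whereas the hypothesis says most of it. Neither p nor f is given in the documents.

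**If 4.0 is already the overall SD.** The base SD (placebo arm and within subgroups) would then be √(16 − p(1 − p)g²/2). With f = 1 this is 3.39 at p = 1/2 and 2.65 at p = 1/3. With p = 1/3 and f = 0.7 it is 3.64. In each of these cases 80% power is kept.

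**The case for a change.** The strongest counter-argument is that the plan calls its target conservative and the trial powered for a clinically significant difference, yet gives the reader no means of checking this. The margin is thin: at 30 completers per group, 80% power is lost once the residual SD passes 4.08. A small responder group carrying nearly all the benefit would cost a good deal of power, and the defence that 4.0 already includes this spread becomes strained. With the whole effect in one quarter of the arm, the base SD would have to be 1.58 (√(16 − 27/2)). At one fifth no base SD works, because 16 − 36/2 is negative. Precision could also be poor. At an assumed SD of 6 with 30 per group, the 95% confidence interval has a half-width of about 2.00 × 6 × √(2/30) = 3.1 points, so an observed difference of zero would not exclude a 3-point benefit.

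The arithmetic in all of this is right, and it stands as a comment on reporting: the SD, its source, and whether it is raw or residual would have been useful to state. It does not show a shortfall. Each unfavourable figure depends on an SD, a responder share or a concentration of effect that the reader has to supply, and less extreme choices leave power close to 80%. Nor does any part of the plan say that a non-significant result would be read as ruling out 3 points.

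**Conclusion.** The concern does not call for a change. The 29 per group is consistent with the stated alpha, power and difference at a residual SD of about 4.0 or less (4.08 at the expected 30 completers per group), and the allowance for dropout is correct. Hypothesis 1a is qualitative. It would tend to widen the aspirin arm, but it does not contradict an SD of 4.0, which may be the overall figure. If 4.0 is instead taken as the base SD, the loss ranges from under 1 percentage point (half the arm carrying 60% of the effect) to about 31 points (one fifth carrying all of it), and nothing in the documents points to a particular value in that range. These figures assume a two-sample comparison and individual gains that are independent of the underlying outcome.

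The gap is one unreported planning input. Supplying it would leave the enrolment target, the primary ANCOVA and its type I error as they are. When the trial is read, the observed residual SD and the confidence interval for the treatment difference will show its actual precision, whatever SD was assumed beforehand.

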## **II. Specific Aims:**

The primary aims of this study are:

**Aim 1:** To evaluate the clinical effect of aspirin augmentation on depression.

**Aim 1a:** To examine the effect of aspirin augmentation on depression symptoms (as measured by the Hamilton Depression Rating Scale) in comparison to placebo augmentation of antidepressant treatment.

**Aim 1b:** To examine the effect of aspirin augmentation on the rapidity of change in depression symptoms (as measured by the Hamilton Depression Rating Scale).

**Aim 2:** To assess with Luminex immunoassay the inflammatory profile of the blood of the aspirin augmentation responders compared with the non-responders.

**Aim 2a:** To determine whether elevated serum inflammatory cytokines IL-6 and TNF- $\alpha$  at study initiation are associated with treatment response to aspirin.

**Aim 2b:** To determine whether serum inflammatory cytokines IL-6 and TNF- $\alpha$  are lower in the augmentation responders group after treatment than in the augmentation non-responders group after treatment.

**Aim 2c:** To determine whether the ratios of TNF- $\alpha$ :IL-10 and IL-6:IL-10 are associated with treatment response versus non-response.

**Aim 3:** To evaluate in an exploratory fashion whether other cytokines/chemokines or immune gene expression patterns at study initiation are associated with subsequent antidepressant response to aspirin.

**Aim 3a:** To assess the panel of 60 cytokines/chemokines in the aspirin augmentation responders compared with the non-responders for potential contributions to treatment responsiveness. This analysis is exploratory.

**Aim 3b:** To assess with Fluidigm technology the blood of the aspirin augmentation responders compared with the non-responders for RNA from three flow sorted subsets of activated memory CD4 $^{+}$  (CD3 $^{+}$ CD44 $^{\text{hi}}$ ), and CD8 $^{+}$  (CD3 $^{+}$ CD44 $^{\text{hi}}$ ) T cells, as well as CD14 $^{+}$  monocytes. 96 T cell or monocyte-specific genes for pro-inflammatory, anti-inflammatory, chemokine, chemokine receptor, and signaling molecules will be measured. This analysis is exploratory.

**Aim 4:** To collect samples for eventual detailed immunologic characterization including antigen arrays and microRNAs.

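### The week-8 IL-6/TNF-alpha outcome is framed as responders versus non-responders with no cut-off or model, although the baseline-marker models use continuous HDRS change

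*Combined protocol and SAP*

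**What the plan says.** The plan has one document, the combined protocol and SAP.

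- **Section VI, Biostatistical Analyses**, names as a secondary outcome "the response of inflammatory biomarkers in treatment responders v. treatment non-responders at 8 weeks".
- **Section II, Aim 2b**, asks whether serum IL-6 and TNF-alpha "are lower in the augmentation responders group after treatment than in the augmentation non-responders group after treatment". Hypothesis 2b predicts that they will be.
- **Section II, Aim 2**, the parent aim, concerns "the inflammatory profile of the blood of the aspirin augmentation responders compared with the non-responders". This points to the aspirin arm, but Section VI does not restrict the outcome to that arm.
- **Section VI**, in the sentence after the secondary outcome, sets an ANCOVA relating V1 levels of IL-6 and TNF-alpha "with change in HDRS from V1 to V4 in the aspirin treated group versus the placebo treated group". Its terms are treatment, baseline cytokine and their interaction. A similar model is planned for the baseline IL-10 ratios. HDRS change is continuous here, but the markers are V1 values only.
- **Section VI** also states: "All applicable tests will be two-tailed with an alpha set at 0.05".

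The documents do not define a responder or give an expected responder share. They specify no test or model for the week-8 markers.

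**The concern.** The only stated form of the week-8 outcome is a two-group contrast formed from the HDRS. A split treats subjects just either side of the cut as different and everyone on one side as alike. The continuous score is already collected and is already the outcome of the baseline-marker models, so the week-8 question could be answered without discarding it.

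Two things are at stake. The first is power, in a comparison that rests on about 30 subjects (aspirin arm) or 60 (both arms). The second is that the result depends on a threshold the plan does not fix, which could be chosen after the data are seen.

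**Working it through.** **1. The plan's own figures.** The documents give no power or information figure for the biomarker comparisons. The only sample-size statement is for the primary outcome: "this study is powered to detect a 3-point difference in HDRS score", with 29 per group, power 0.80 and two-sided alpha 0.05. No SD is given, so 29 can only be solved backwards: SD = 3 × √(29/2) / (1.960 + 0.842) = 4.08 (normal approximation), or 4.01 with the t distribution. That is a separate matter and is not used below.

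Completers: 74 × 0.80 = 59.2, stated as 60. Per arm: 37 × 0.80 = 29.6, about 30.

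**2. Information kept by a split.** Assume HDRS change and the marker (on a suitable scale) are jointly normal. With a share p of subjects above the cut, the efficiency relative to the continuous score is

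E(p) = φ(z_p)² / [p(1 − p)].

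| Responder share p (assumed) | Calculation | E(p) | Loss | Effective n of 60 | Effective n of 30 |
|---|---|---|---|---|---|
| 50% | 0.3989² / 0.25 | 0.637 | 36.3% | 38.2 | 19.1 |
| 40% | 0.3863² / 0.24 | 0.622 | 37.8% | 37.3 | 18.7 |
| 30% | 0.3477² / 0.21 | 0.576 | 42.4% | 34.5 | 17.3 |
| 20% | 0.2800² / 0.16 | 0.490 | 51.0% | 29.4 | 14.7 |

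Under this model an even split loses least, so 36% is the minimum loss for any single cut. Shares of 15% and 10% would lose 57.4% and 65.8%. The percentage does not depend on n.

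**3. Power.** Assume a true correlation of 0.35 between HDRS change and the week-8 marker; the documents give none. The figures below are simulated (20,000 runs per setting, two-sided 0.05), with a correlation test for the continuous score and a two-group t-test for the split.

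| n | Continuous | Split, p = 50% | Split, p = 30% | Split, p = 20% |
|---|---|---|---|---|
| 60 (both arms) | about 80% | 60% | 54% | 48% |
| 30 (aspirin arm) | about 48% | 32% | 30% | 25% |

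A hand check uses the attenuated correlation r_s = 0.35 × √E(p) and power ≈ Φ(atanh(r_s) × √(n − 3) − 1.96):

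- Continuous, n = 60: Φ(0.365 × 7.55 − 1.96) = 79%.
- p = 50%, n = 60: r_s = 0.279, power 58%.
- p = 20%, n = 60: r_s = 0.245, power 47%.
- n = 30, in the same order: 48%, 32% and 25%.

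These agree with the simulation to within about 1 to 2 points.

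**4. What the continuous analysis can detect.** The smallest correlation detectable with 80% power is tanh(2.80/√(n − 3)): 0.35 for n = 60 and 0.49 for n = 30. The aspirin-arm question therefore stays weakly powered even without a split.

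**5. A different model.** Suppose instead that there are two true classes: 40% responders, a marker shift of 0.8 SD, n = 60, and a cut midway between the classes on HDRS.

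| HDRS separation of the classes | Continuous | Split |
|---|---|---|
| 2 SD | 51% | 48% |
| 3 SD | 67% | 70% |
| 4 SD | 74% | 80% |

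The loss in step 2 then nearly vanishes or reverses.

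**The case against.** **Hypothesis 1a expects a responder subgroup.** It says that such a subgroup will account for most of the aspirin signal. If response is truly a class, a contrast between classes is a reasonable target, and step 5 shows that a well-placed cut costs little or even gains. This stands as a limit on the size of the loss. It does not rescue the plan as written, because the plan gives no rule for finding the class and its own baseline models treat response as continuous.

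**No split test is actually specified.** A reader might infer that the plan commits to testing two groups at week 8. The wording of the outcome, aim and hypothesis points that way, but the only model that follows covers V1 markers. The defect is therefore partly an omission: cut-off, population and model are all missing. That supports settling them now.

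**Exploratory profiling.** Section VI gives that work the goal "to discern any differences between non-responders and responders", and a reader might infer that the 60-cytokine and 96-gene analyses also split subjects. The documents do not support this. For the cytokine panel, Section VI specifies the interaction of each baseline value with treatment, and it plans a similar procedure for the genes. Those analyses need no change. The post-treatment parts of Hypotheses 3a and 3b are comparisons over time within responders, which is a different question.

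**Conclusion.** The point holds for the week-8 IL-6 and TNF-alpha secondary outcome only. That outcome is framed as a responder contrast with no cut-off or model, while a continuous measure of response is already in hand and already used for baseline markers.

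The loss is about 36% to 51% of the information if HDRS change and marker are jointly normal and 20% to 50% of subjects respond. A reader might take that range as a property of the trial. It is not, because the documents state neither a share nor a cut-off, and the loss could be larger (a share below 20%) or close to nil (a discrete class, well separated).

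Nor is 60 clearly the right base. Aim 2 reads most naturally as the aspirin arm, about 30 completers, where even the continuous analysis has only about 48% power at a correlation of 0.35. The proposed change recovers information but does not make this aim well powered.

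**What to change.** For the week-8 secondary outcome, specify in Section VI:

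1. A model with week-8 IL-6 (and separately TNF-alpha) as the outcome. Its terms are the marker's baseline value, continuous HDRS change from V1 to V4, treatment, and the interaction of HDRS change with treatment.
2. The aspirin-arm slope from that model as the Aim 2b result, which settles the population. The power figures in the working are for a simple correlation, so they are only a guide to this adjusted slope.
3. The responder versus non-responder comparison as a descriptive or supportive analysis, with the cut-off fixed in advance.

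This needs no new data, visits or assays. The cost is that Aim 2b and Hypothesis 2b must be reworded from a group contrast to an association between HDRS change and week-8 marker level. Leave the baseline 60-cytokine and 96-gene analyses as they are.
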